5.1 Inclusion criteria

Participants eligible for inclusion in this study must meet all of the following criteria:

- 1. Signed informed consent from the participant must be obtained prior to participation in the study.
- 2. At Screening, participants will be educated on facts about *Cryptosporidium* disease, safety measures and transmission risks. Participants must then score 100% on a quiz assessing their understanding of *Cryptosporidium* infection and transmission. Participants will have the opportunity to retake the quiz. The quiz should be repeated before any additional Screening assessments are obtained.
- 3. Male and female participants must be between 18 to 50 years of age and in good health as determined by medical history, physical examination, vital signs, electrocardiogram, and laboratory tests at Screening and Baseline.
- 4. At Screening and Baseline, vital signs will be assessed in the sitting position, and must be within the following ranges:
 - oral body temperature between 35.0-37.0 °C
 - systolic blood pressure between 90-139 mmHg
 - diastolic blood pressure between 59-89 mmHg
 - pulse rate between 50-90 bpm
- 5. Participants must weigh at least 50 kg, and have a body mass index (BMI) within the range of $18-30 \text{ kg/m}^2$.

Amended Protocol Version V02 (Clean)

- 6. Ability to communicate well with the Investigator, and to understand and comply with the requirements of the study including restrictions provided in Section 6.2.4.
- 7. Participant must be in compliance with current local COVID-19 testing policies.

5.2 Exclusion criteria

Participants meeting any of the following criteria are not eligible for inclusion in this study.

No additional exclusions may be applied by the Investigator, in order to ensure that the study population will be representative of all eligible participants.

- 1. History of Cryptosporidium infection.
- 2. Current (based on screening laboratory tests) or history of infectious diarrhea associated with international travel in the last 12 months or *C. difficile* infection within 6 months prior to Screening.

Page **31** of **81** Protocol No. CABO809A02101

Page **32** of **81** Protocol No. CABO809A02101

Commercially Confidential Information

6 Treatment

6.1 Study treatment

Details on the requirements for storage and management of study treatment, and dispensing and taking study treatment will be outlined in the Pharmacy Manual. If vomiting occurs within 30 minutes of administration of ABO809 a second administration of ABO809, at the same dose may be given.

6.1.1 Investigational and control drugs

Table 6-1 Investigational drug

Investigational Drug (Name and Strength)	Pharmaceutical Dosage Form	Route of Administration	Supply Type
ABO809, 3x10 ⁶ CE/3 mL	Concentrate for oral suspension	Oral use	Open label bulk supply; glass vials

CE, C. parvum oocysts

No control drug will be used in this study.

6.1.2 Additional study treatments

Participants may receive nitazoxanide (see Section 6.2.3).

Table 6-2 Additional Study Treatment

Drug	Pharmaceutical	Route of	Supply Type
(Name and Strength)	Dosage Form	Administration	
Nitazoxanide 500 mg	Tablet	Oral use	Bottle

Nitazoxanide to be provided by clinical site

6.1.3 Supply of study treatment

Refer to Pharmacy Manual.

6.2 Other treatment(s)

Participants may receive nitazoxanide and/or other treatments as detailed below.

6.2.1 Concomitant therapy

All medications, procedures, and significant non-drug therapies (including physical therapy and blood transfusions) administered after the participant is enrolled into the study must be recorded on the appropriate Case Report Forms. Fluid replacement (e.g. as needed with diarrheal symptoms) will be recorded as a concomitant medication.

Each concomitant medication must be individually assessed against all exclusion criteria/prohibited medication. If in doubt, the Investigator should contact the Novartis medical monitor before administering a new medication.

6.2.2 Prohibited medication

Except for protocol allowed concomitant medication or any medication which may be required to treat adverse events, no medication other than study treatment will be allowed from the date the participant signs the inform consent until EOS.

Participants should not receive any antiperistaltic, antidiarrheal agents or stool softeners from Screening through Day 28. These agents include, but are not limited to, bismuth subsalicylate, atropine and diphenoxylate, loperamide, octreotide, opium tincture, cholestyramine, colestipol, colace, or lactulose. Participants should not consume yogurt, kefir or probiotics (e.g. *Saccharomyces boulardii*) up to Day 21 or initiation of nitazoxanide, whichever comes first. All medications, procedures and significant non-drug therapies (including physical therapy and blood transfusions) administered after the participant is enrolled into the study must be recorded on the appropriate Case Report Forms.

In addition, other than those administered per protocol, participants should not receive any antibacterial or anti-parasitic therapy with possible activity against *Cryptosporidium* up to Day 28 (see Section 6.2.3).

Warfarin or drugs that prolong the QTc interval are not permitted between Screening and Day 28 unless deemed necessary by the Investigator (participants on warfarin or drugs that prolong the QTc interval are not permitted to enter the study (see Section 5.2).

Vaccinations are not permitted between Day -14 and Day 28 but are permitted outside this window (including COVID-19 vaccinations).

6.2.3 Rescue medication

To minimize the risk of severe clinical illness, long-term asymptomatic shedding and recurrence of *Cryptosporidium* infection, nitazoxanide may be administered at 500 mg by mouth every 12 hours with food for 3 days as per the U.S. Prescribing Information, under the clinical conditions outlined below. Nitazoxanide is the standard of care for the treatment of cryptosporidiosis. In double-blind, controlled trials in adults and adolescents with diarrhea and with or without enteric symptoms caused by *C. parvum*, nitazoxanide administered at 500 mg BID for 3 days resulted in a 96% clinical response rate 4 to 7 days following the end of treatment. In this study, clinical response was defined as "no symptoms, no watery stools and no more than 2 soft stools within the past 24 hours" or "no symptoms and no unformed stools within the past 48 hours" (Romark 2017).

All participants who receive ABO809 and develop an infection (i.e. oocyst shedding after Day 3), will receive nitazoxanide on Day 21 or as soon as EIA analysis

of Day 17 sample becomes available whether or not they develop clinical symptoms. There are conditions under which participants may receive nitazoxanide earlier: (i) participants with diarrhea persisting until Day 10 will start nitazoxanide on Day 10, (ii) participants with severe diarrheal illness (≥ Grade 3 as per Toxicity Grading Scale for Healthy Adult and Adolescent Volunteers Enrolled in Preventive Vaccine Clinical Trials (2007)) may receive

nitazoxanide unless deemed contraindicated by the Investigator irrespective of timing. Whenever nitazoxanide treatment is administered to participants experiencing clinical symptoms, participants may be domiciled at the discretion of the Investigator until free of clinical symptoms for ≥ 24 hours.

A second course of nitazoxanide and/or other antiparasitic drug(s) (e.g. paromomycin alone or in combination with azithromycin) may be considered for participants with severe diarrhea or treatment failure after nitazoxanide monotherapy at the discretion of the Investigator. The duration of treatment will depend upon the participant's response to therapy. Although controlled, large-scale trials are lacking, the use of combination therapy is supported by findings from small case series (Smith et al 1998). Paromomycin (500 mg three times daily for one week) is generally used as an alternative agent if nitazoxanide cannot be used. All antimicrobial therapy for cryptosporidiosis administered before Day 28 will be recorded in eCRF as a concomitant medication.

Participants will not receive nitazoxanide if:

- they did not shed oocysts at any time after Day 3 and
- they did not have diarrhea between Day 1 and Day 21 and
- there was no diagnosis of cryptosporidiosis in any of the participant's household contacts between Day 11 and Day 21

In participants with severe diarrheal illness, oral and/or intravenous hydration, and replacement of electrolytes as needed, is expected as part of the standard of care management of adverse events (dehydration and severe diarrhea). Fluid replacement therapy will be recorded as a concomitant medication in the eCRF.

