Treatment with nitazoxanide: Nitazoxanide is a safe and well-tolerated drug approved in the United States to treat diarrhea caused by Cryptosporidium parvum. In a 2015 C. muris challenge study, two subjects with persistent oocyst shedding were successfully treated with nitazoxanide and the infection was resolved in both subjects, demonstrating the potential of nitazoxanide as a rescue drug (Chappell et al 2015). Following resolution of diarrhea, C. parvum infection may be associated with shedding of oocysts with a 21% relapse rate as suggested by the 1993 Milwaukee outbreak (MacKenzie et al 1995). Participants who develop an infection (i.e. oocyst shedding), with or without clinical symptoms will receive a standard 3-day course of nitazoxanide treatment per the U.S. Prescribing Information on Day 21. Given the variability in the onset and duration of oocyst shedding and clinical symptoms in healthy adults. administering nitazoxanide on Day 21 is considered appropriate to enable the full characterization of the study endpoints. Nitazoxanide may be administered earlier, based on clinical findings (see Section 3.3 and Section 6.2.3). Once initiated, nitazoxanide treatment is expected to decrease or eliminate any persistent oocyst shedding to safeguard participants, their household contacts and public health interests. Participants will be informed about reasons of nitazoxanide treatment to improve compliance, which will be recorded in a participant diary. Although nitazoxanide has proven efficacy in reducing oocyst shedding and acute diarrhea in 80-93% of treated participants, there have been no studies looking at the effect of nitazoxanide on the incidence of long-term oocyst shedding or sequelae of cryptosporidiosis. Given this background, Safety Follow-Up Calls will be conducted up to Day 56.

Adaptive study design: The goal is to maximize the incidence of infection. The study cohorts of approximately 10 participants each are designed to enable domiciling of participants in an inpatient unit with adequate infection control, isolation and monitoring. Cohorts are sequential to enable adjustment of the ABO809 dose from one cohort to the next for efficacy and safety reasons. After the Day 14 visit, a Dose Adjustment Data Review will be conducted for the

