Potential adverse events from Nitazoxanide therapy: Nitazoxanide (Alinia[®]) will be administered to all participants with Cryptosporidium positive stool and/or clinical symptoms on Day 21. Nitazoxanide may be administered earlier to participants with persistent diarrhea on or after Day 10 to resolve diarrheal illness and minimize the risk of shedding or recurrent disease. To avoid unnecessary medication, participants without oocyst shedding at any time after Day 3 and without any diarrhea between Day 1 and Day 21 and without household contacts with diarrhea between Day 10 and Day 21 will not receive nitazoxanide. Nitazoxanide may also be administered as part of "rescue medication" to treat severe diarrheal illness before Day 10 (see Section 6.2.3). The most common adverse reactions in >2% of patients were abdominal pain, headache, chromaturia and nausea. In placebo-controlled clinical trials using the recommended dose of nitazoxanide, the rates of occurrence of these events did not differ significantly from those of the placebo. In controlled trials of patients age 12 years and older who received nitazoxanide for the treatment of diarrhea caused by Giardia lamblia or C. parvum, less than 1% of patients discontinued therapy because of an adverse event (Romark 2017). In the unlikely event that symptoms persist, the participant will, at the discretion of the Investigator, obtain additional diagnostic work-up and subsequent therapy (potentially including a second course of nitazoxanide) as appropriate (see Section 6.2.3).

The risks to participants in this trial may be minimized by compliance with the eligibility criteria and study procedures, as well as close monitoring. Refer to the Investigator's Brochure.

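### The documents conflict on when nitazoxanide starts and when it is withheld, and the secondary endpoints are censored at that start

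*Protocol*

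**What the plan says.** **Diarrhea persisting to Day 10.** Protocol 6.2.3 states that "participants with diarrhea persisting until Day 10 will start nitazoxanide on Day 10"; SAP 2.3.4 has the same sentence. In both, this mandatory clause sits in a list introduced as conditions under which participants *may* be treated earlier. Protocol 4.5 says: "Nitazoxanide may be administered earlier to participants with persistent diarrhea on or after Day 10". Protocol 4.1 and SAP 1.1 say only that the drug may be given earlier on clinical findings.

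**Infected participants in general.** Under Protocol 4.1 they "will receive a standard 3-day course of nitazoxanide treatment per the U.S. Prescribing Information on Day 21". The Protocol summary, the schedule in Table 8-1 and the first statement of SAP 2.3.4 also give Day 21. Protocol 6.2.3 says they "will receive nitazoxanide on Day 21 or as soon as EIA analysis" of the Day 17 sample is available, with or without symptoms, and the second statement of SAP 2.3.4 repeats this. Protocol 3.3 and SAP 1.1 say only that participants may receive the drug.

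**Withholding.** Protocol 4.5 says that participants with no shedding, no diarrhea and "without household contacts with diarrhea between Day 10 and Day 21 will not receive nitazoxanide". The third condition in Protocol 6.2.3 and SAP 2.3.4 is instead that "there was no diagnosis of cryptosporidiosis in any of the participant's household contacts between Day 11 and Day 21".

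**Analysis.** SAP 2.5.3 censors all Kaplan-Meier analyses at rescue, right-censors the day counts, durations and stool weight, and sets stools graded below 3 after rescue to missing. SAP 2.4.3 sets negative infection results after rescue to missing in the time profiles.

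**The concern.** Time to resolution and the duration of illness and shedding describe the natural course that this infection model is meant to establish. All of them are cut at the first dose of nitazoxanide. If one passage requires a start on Day 10, another allows it from Day 10 onward, and others point to Day 17 or Day 21, the observable part of the course depends on which passage is followed.

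The *will* and *may* readings also produce different kinds of censoring. Under *will*, everyone with diarrhea persisting to Day 10 is cut at the same day. Under *may*, the choice of whom to treat is likely to follow the course of illness, so the censoring is probably informative and the Kaplan-Meier estimates harder to interpret.

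The withholding conditions raise a separate matter: whether some healthy volunteers with neither shedding nor diarrhea may be given a drug, when Protocol 4.5 states an aim of avoiding unnecessary medication.

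**Working it through.** The plan states no figure for this point, so there is none to reproduce. The check compares the passages and then asks how many participants the difference could reach.

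**Step 1. Untreated follow-up.** Dosing is on Day 1, so days since dosing = study day - 1.

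| Start of nitazoxanide | Untreated days |
|---|---|
| Day 10 | 10 - 1 = 9 |
| Day 17 sample result | 17 - 1 = 16 or more (laboratory turnaround is not stated) |
| Day 21 | 21 - 1 = 20 |
| Not treated, followed to Day 28 | 28 - 1 = 27 |

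For diarrhea persisting to Day 10, the passage followed can move the start by up to 21 - 10 = 11 days. For other infected participants it can move it by up to 21 - 17 = 4 days.

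**Step 2. Is illness at Day 10 common?** Four rows of Protocol Table 4-1 give one incubation and one duration each (means and medians are mixed, so this is a rough guide). Onset study day = incubation + 1; end = onset + hours/24.

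| Table 4-1 row | Incubation, duration | Average course (study days) |
|---|---|---|
| Iowa, first | 6.5 d, 74 h | 7.5 to 10.6 |
| Iowa, second | 8.2 d, 60 h | 9.2 to 11.7 |
| Iowa, third | 5 d, 155 h | 6.0 to 12.5 |
| UCP | 6 d, 56 h | 7.0 to 9.3 |

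In the three Iowa rows the average course is still running on Day 10; in the UCP row it is not.

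**Step 3. Share still ill at Day 10.** Assumptions: gamma-distributed onset with the row's incubation as mean and SD 2 or 3 days; duration with the row's value as mean, either exponential or gamma with coefficient of variation 0.5. The quantity is P(onset ≤ 9 d and onset + duration > 9 d), from 400,000 draws per scenario.

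| Table 4-1 row | Range over the four scenarios |
|---|---|
| Iowa, first | 30-45% |
| Iowa, second | 28-43% |
| Iowa, third | 46-68% |
| UCP | 21-28% |

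Overall this is about 21-68%. The documents do not define how long diarrhea must have lasted to count as persisting. If onset must be at least one day before the cut, the range is about 15-64%.

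**Step 4. Participants.** Protocol 6.5.1 continues a dose at roughly 60-70% diarrheal illness. If that is reached in 30 participants, 0.60 × 30 = 18 to 0.70 × 30 = 21 are ill. Then 18 × 0.21 = 3.8 and 21 × 0.68 = 14.3, so about 4 to 14 would be cut at Day 10 under the mandatory wording, and possibly none under the optional wording.

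**Step 5. Withholding.** Take a participant with no shedding and no diarrhea whose household contact has undiagnosed diarrhea on Day 15. All three conditions of 6.2.3 are met, so treatment is withheld. The condition in 4.5 is not met, so 4.5 does not withhold it. The windows also differ by a day (Day 10 or Day 11). In addition, 4.5 treats on clinical symptoms alone, whereas the routine Day 21 rule in the Protocol summary, 4.1, 6.2.3 and SAP 2.3.4 is tied to infection.

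**The case against.** The best defense is that Day 21 is a default and 6.2.3 is the operative section. Section 4.1 says that "administering nitazoxanide on Day 21 is considered appropriate to enable the full characterization of the study endpoints", but it then allows earlier use on clinical findings and refers to 3.3 and 6.2.3. This stands: a reader might infer that 4.1 rules out any Day 10 start, and it does not. It leaves two conflicts. The verb for Day 10 still differs between 6.2.3 and 4.5, and the Day 17 rule applies regardless of symptoms, so the clinical-findings exception does not cover it.

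Other stronger readings are also unsupported:

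- That 6.2.3 leaves a non-severe illness starting on Day 11 without any trigger before Day 21. If the participant is infected, the Day 17 result reaches it. Handling it differently from illness present at Day 10 is a feature of 6.2.3, not a contradiction.
- That 4.5 requires a positive stool on Day 21 itself. There, Day 21 can equally be the day of administration, and the same paragraph's exclusion looks at shedding at any time after Day 3. Only the symptoms-alone route differs. Even there, the withholding list in 6.2.3 does not exclude a participant who had diarrhea without shedding.
- That the household condition alters time to resolution or duration. It applies only to participants with neither shedding nor diarrhea. Nor does 4.5 positively order treatment for them; the conflict is between two withholding lists.
- That all data after rescue are lost. Positive infection results and stools graded 3-5 are not set to missing.
- That 16-75% of ill participants are affected. Those extremes pair an incubation from one study with a duration from another (5 d with 56 h; 6.5 d with 155 h).
- That cohorts will in fact be handled differently. The study is single-center; this is possible but not shown.

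**Conclusion.** The concern holds for three conflicts in current text: the Day 10 rule, the Day 17 or Day 21 start, and the condition for withholding. The SAP does not settle them, because its Sections 1.1 and 2.3.4, and the two statements within 2.3.4, differ among themselves.

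The first two conflicts change untreated follow-up between 9, at least 16 and 20 days for endpoints that are censored at rescue. About 21-68% of ill participants could be exposed to the Day 10 conflict. That range rests on assumed distributions, on treating Table 4-1 averages as means, and on past strains and doses resembling this study. The count of 4 to 14 per 30 further assumes that the 60-70% illness target is reached; diarrhea incidence in Table 4-1 runs from 0 to 86%.

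The primary endpoint, infection up to Day 10, is barely affected: only samples taken after a Day 10 start or after earlier rescue could matter, unless the window is extended as Protocol 12.4 allows. The withholding conflict bears on who may receive the drug, not on the duration endpoints. This is an inconsistency that should be corrected, not a flaw in the primary result.

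**What to change.** The sponsor and investigator should reconcile the passages into a single rule that states the verb (will or may), the start day, who is eligible, and one household-contact criterion with its dates. The same text should then appear in the Protocol summary, Protocol 3.3, 4.1, 4.5, 6.2.3 and Table 8-1, and in SAP 1.1 and 2.3.4. Which rule is right is for them to decide; none is proposed here.

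No new eCRF field is needed. Censoring under SAP 2.5.3 depends on whether and when rescue was taken, not on the reason, and Table 8-1 (footnote 8) already has nitazoxanide recorded on the concomitant medication page.

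The cost is a protocol wording amendment with its usual approvals and matching SAP text, with no extra participants, samples or procedures.

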6.2.4 Restriction for study participants

Participants should be informed and reminded of the restrictions outlined in this section.

6.2.4.1 Dietary restrictions and smoking

- No alcohol from Day-2 until after the Day 28 visit.
- No cannabis use from Screening until after the Day 28 visit.
- No cigarettes/use of nicotine products from Screening until the Day 28 visit.
- Only thoroughly cooked meat, fish and seafood will be allowed from Day-4 until after the Day 28 visit (all meat must be "well done" so that no red is evident).
- Participants should not consume yogurt, kefir or probiotics (e.g. *Saccharomyces boulardii*) up to Day 21 or initiation of nitazoxanide, whichever comes first.

Meals will be provided when all study procedures scheduled for that time have been completed.

6.2.4.2 Other restrictions

- No strenuous physical exercise (e.g. weight training, aerobics, football) from Day 1 until discharged
- Participants must abstain from using public pools and waterparks from Day 1 until after the Day 28 visit. Refraining from using private swimming pools is also recommended.

- Employment as a healthcare worker with direct patient care, in a daycare center (for children or the elderly), or direct food handler (individuals who work directly with food in commercial establishments) is prohibited between Screening and Day 28.
- Sharing a home with a pregnant woman or anyone <7 years old or >65 years old, infirmed, or immunocompromised is prohibited between Screening and Day 28.
- Sexual practices that may increase the risk of fecal-oral transmission of *Cryptosporidium* should be avoided or appropriate safety measures used from Day 1 until after the Day 28 visit. Participants will be informed about CDC recommendations to practice safer sex in case of cryptosporidiosis.

(Parasites-Cryptosporidium-Prevention & Control-General Public 2019):

- Wait to have sex (vaginal, anal, and oral) for 2 weeks after you no longer have diarrhea
- Reduce your contact with stool during sex by:
 - Washing your hands, genitals, and anus with soap and water before and after sexual activity
 - Using barrier methods during sex. Barrier methods include condoms, dental dams, and cut-open condoms. Sex includes oral (mouth-to-penis, mouth-to-vagina, mouth-to-anus), anal (penis-to-anus), and vaginal (penis-to-vagina) sex
 - Using latex gloves during anal fingering or fisting
 - Using condoms the right way, every time you have anal and vaginal sex, which will also help prevent other sexually transmitted infections
 - Washing your hands with soap and water immediately after touching a used condom or other barrier method
 - Washing sex toys with soap and water after each use, and washing hands after touching used sex toys

Participants will receive educational material explaining all applicable restrictions and recommendations to avoid spread of *Cryptosporidium* oocysts.

